4.1.1. Screening Period

In order to facilitate enrollment and decrease unnecessary blood sampling, it is recommended to start the screening process with the assessment of the AAV2/6 serological status only (Section 8.2.13.1). If the participant qualifies, then the rest of the screening tests (total duration approximately 8 weeks) will be performed.

All screening assessments are listed in the SoA table (Table 1). A participant must meet all Inclusion Criteria, and none of the Exclusion Criteria, to participate in this study.

4.1.2. Treatment Period

This study will follow an adaptive, dose escalation and participant enrollment design to establish and enroll participants at a dose level that can achieve therapeutically useful FVIII levels comparable with emerging gene therapies (in the 10-150% range), with a therapeutic goal of FVIII activity of 40-100% of normal. The schema aims to minimize enrollment to dose levels that are inactive or results in FVIII levels of >150%.

One (1) participant will initially be enrolled at a given dose level and followed over 6 weeks. After review of safety data for the first participant, a second participant will be enrolled at the same dose level and also followed for 6 weeks. Then DMC will meet and recommend dose escalation, dose de-escalation, or cohort expansion.

The possible clinical dose level range will be from 6×10^{11} vg/kg to 6×10^{13} vg/kg, with a starting dose of 9×10^{11} vg/kg, which is expected to yield >5% normal FVIII levels in 57% of treated participants. Several dose levels may need to be studied to identify a safe and tolerable therapeutic range. If observed FVIII levels at the starting dose level of 9×10^{11} vg/kg are higher than anticipated, then dose de-escalation to 6×10^{11} vg/kg will be considered. The planned dose escalation interval between dose levels is roughly 2-fold (0.33 log).

Participants will be dosed with one of 12 potential dose levels, as outlined in the table below:

Possible Total rAAV Dose (vg/kg)
6×10^{11}
9×10^{11}
1.2×10^{12}
2×10^{12}
4×10^{12}
6×10^{12}
1×10^{13}
2×10^{13}
3×10^{13}
4×10^{13}

Possible Total rAAV Dose (vg/kg)
5×10^{13}
6×10^{13}

The starting dose level (9×10^{11} vg/kg) was associated with FVIII activity of 12% of normal in a NHP study. Unless more are recommended by the DMC, approximately 20 participants are planned to be dosed in this clinical trial.

Based on DMC review of safety and pharmacodynamics (PD) data, additional participants may be enrolled at a specific dose level. The dose selected will be a tolerable dose level where FVIII activity does not exceed 150% based on observed activity and variability.

4.1.2.1. Dose Escalation Based on Pharmacodynamic Response

The dose escalation plan and participant assignment to dose levels will be according to an analysis of FVIII expression response based on weekly longitudinal FVIII activity measurements. At the end of the first cohort, safety and expression data will be available for 2 participants over 12 and 6 weeks, respectively. The DMC will review all the safety data and will recommend, based on this review and the expression levels, to move to a different dose level, de-escalate or expand the current one.

While these guidelines use mean FVIII activity results within dose levels, the DMC must also be consulted if any participant at a given dose level has FVIII peak activity of >150% prior to adding further participants.

4.1.2.2. Dose Escalation Based on Safety

Determination of Dose limiting toxicities (DLTs) will be made by the DMC (Section 9.6). Further enrollment to a dose level and dose escalation based on PD response per the above schema will be modified for reasons of safety based on the guidelines below:

- If at any given dose level, >50% participants experience a DLT, additional participants can only be enrolled at that dose level in concert with the DMC.
- Escalation to a higher dose level can only occur if not more than 40% of participants, and at least 2 participants experience a DLT.
- An average FVIII expression of 150% or more will be considered as a safety issue and the DMC may consider dose de-escalation.

Safety data will take precedence over expression data for dose escalation. If further enrollment in a cohort for safety reasons is prevented by insufficient expression data, the DMC and sponsor will adjudicate the circumstances for further participant enrollment.

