4. STUDY DESIGN

4.1. Overall Design

This study is a phase 1/2, open-label, single-dose, dose-ranging study. The dose selection and number of participants studied at each dose level will be based on safety and kinetics of circulating FVIII levels observed in previously dosed participants.

The adaptive design of this phase 1/2 study assigns participants to SB-525 (PF-07055480) dose levels based on the average of FVIII expression in the 2 first participants of a cohort.

For each cohort, the first dosed participant will be followed for 6 weeks before a second participant can be dosed. After the second participant in a cohort is followed for 6 weeks, the Data Monitoring Committee (DMC) will meet and recommend either a dose escalation, dose de-escalation, or cohort expansion (with potential reassessment of participant's data) based on their review of the cumulative data available from the first 2 participants of a cohort.

The duration of study participation will be approximately 62 months for each participant, divided into approximately 8 weeks (2 months) for screening, and 60 months for treatment and study follow-up.

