### **6.5.3. Study Treatment Exposure**

The total amount of IP taken by participant (vg) will be summarized for the Safety population by dose level. The number and percent of participants receiving the intended dose and experiencing interruptions during dosing will also be summarized. The doses corresponding to the 4 cohorts are: 9x10^11vg/kg (cohort 1), 2x10^12vg/kg (cohort 2), 1x10^13vg/kg (cohort 3), and 3x10^13vg/kg (cohort 4).

A listing of IP administration will be created.

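### The DLT escalation rule as printed requires at least 2 participants with a DLT, which no cohort of 2, 3 or 4 can meet under the 40% cap; the plausible intended rules disagree at 1 of 2 and 2 of 5

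*Protocol*

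**What the plan says.** Protocol 4.1.2.2 lists safety conditions under which enrolment to a dose level and escalation "will be modified for reasons of safety based on the guidelines below". The escalation condition reads: "Escalation to a higher dose level can only occur if not more than 40% of participants, and at least 2 participants experience a DLT". The bullet before it concerns further enrolment at the same dose: "If at any given dose level, >50% participants experience a DLT, additional participants can only be enrolled at that dose level", with the DMC's involvement. The third bullet concerns average FVIII expression of 150% or more and sets no DLT limit. The DMC decides what counts as a DLT.

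The timing of the decision is set elsewhere. Protocol 4.1 has the DMC recommend escalation, de-escalation or expansion "based on their review of the cumulative data available from the first 2 participants of a cohort". Protocol 4.1.2 says the same of the point when the second participant has been followed for 6 weeks: "Then DMC will meet and recommend dose escalation, dose de-escalation, or cohort expansion". Expansion is open-ended: "Based on DMC review of safety and pharmacodynamics (PD) data, additional participants may be enrolled at a specific dose level".

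The SAP does not restate the DLT rule. SAP 6.5.3 lists four cohorts at rising doses, from 9×10^11 to 3×10^13 vg/kg.

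**The concern.** The sentence joins a ceiling on the DLT share to a floor on the DLT count and makes both conditions for escalating. A floor on toxicity is perverse: it bars escalation from a clean cohort and permits it only when some toxicity has been seen. It also conflicts with the design, which expects an escalation decision at 2 participants.

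This is the only numeric DLT limit on escalation in the protocol. If it cannot be followed as printed, the DMC and later readers must guess the intended rule. The guess matters most at 1 DLT in 2 participants, because 2 is the scheduled review size. The dose path ends at the level that SAP 3.1.2.1 describes as intended for Phase 3, so readers of the study report will want to know how that level was reached.

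**Working it through.** **Inputs.** The 40% ceiling and the count of 2 come from Protocol 4.1.2.2; the review size of 2 from Protocol 4.1 and 4.1.2. Expansion has no fixed size, so larger cohorts were enumerated as well. The documents give no DLT rate, and no sample size, power or error rate is attached to this rule, so there is no stated figure to reproduce.

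Let k be the number of participants with a DLT out of n.

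**Step 1: the rule as printed.** Escalate only if k/n ≤ 0.40 and k ≥ 2. The smallest count allowed by the second condition is k = 2:

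- n = 2: 2/2 = 100%, fails
- n = 3: 2/3 = 66.7%, fails
- n = 4: 2/4 = 50%, fails
- n = 5: 2/5 = 40%, passes, and only at k = 2 (3/5 = 60%)

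No outcome permits escalation at n = 2, 3 or 4, and k = 0 fails at every n. At n = 5 the probability of meeting the rule is 10p²(1−p)³ for a true DLT probability p. With assumed p of 5%, 10%, 30% and 40% it is 0.02, 0.07, 0.31 and 0.35, so over this range the chance of escalating rises with toxicity.

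**Step 2: what may have been meant.**

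- **A, paired threshold:** escalation is barred only if k/n > 0.40 and k ≥ 2.
- **B, ceiling plus a low count:** escalation needs k/n ≤ 0.40 and k < 2.
- **C, minimum number assessed:** escalation needs n ≥ 2 and k/n ≤ 0.40.

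DLT counts that permit escalation:

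| n | As printed | A | B | C |
|---|---|---|---|---|
| 2 | none | 0, 1 | 0 | 0 |
| 3 | none | 0, 1 | 0, 1 | 0, 1 |
| 4 | none | 0, 1 | 0, 1 | 0, 1 |
| 5 | 2 | 0, 1, 2 | 0, 1 | 0, 1, 2 |
| 6, 7 | 2 | 0, 1, 2 | 0, 1 | 0, 1, 2 |
| 8, 9 | 2, 3 | 0 to 3 | 0, 1 | 0 to 3 |

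For n = 2 to 5, A, B and C differ at two outcomes only: 1 of 2 (A allows; B and C bar) and 2 of 5 (A and C allow; B bars). In larger cohorts B also differs from A and C at 2 of 6, 2 of 7, and 2 or 3 of 8 and of 9.

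**Step 3: does other text decide?** The >50% bullet has the flavour of A, but 1 of 2 is exactly 50%, so it is not triggered; it also governs enrolment at the same dose, not escalation. The ALT thresholds in Protocol Appendix 7 concern steroid prophylaxis and when to involve the DMC.

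**Step 4: how often the scheduled review would meet the ambiguous outcome.** P(exactly 1 of 2) = 2p(1−p), with p assumed:

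- p = 0.05: 2 × 0.05 × 0.95 = 0.095
- p = 0.10: 2 × 0.10 × 0.90 = 0.180
- p = 0.20: 2 × 0.20 × 0.80 = 0.320
- p = 0.30: 2 × 0.30 × 0.70 = 0.420

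At n = 2, the probability that escalation is allowed is 1−p² under A and (1−p)² under B or C: 0.99 against 0.81 at p = 0.10, and 0.91 against 0.49 at p = 0.30.

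**The case against.** The strongest reply is that this is a drafting slip that no DMC would apply literally. The bullets are called guidelines, and Protocol 4.1.2.1 gives the DMC a full review: "The DMC will review all the safety data and will recommend, based on this review and the expression levels". Safety takes precedence over expression, and no reading triggers automatic escalation. If a cohort with 1 of 2 were expanded to 3 or 4 without another DLT, all three readings would allow escalation. The DMC charter, which is not available here, may hold the operating rule. SAP 6.5.3 ("The doses corresponding to the 4 cohorts are") names four set doses, so the decisions appear to be past, and the analyses are purely descriptive (SAP 5.1).

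Reading B is also the weakest. With fewer than 2 DLTs the share is at most 1/3 once n is 3 or more, so the 40% ceiling would matter only at 1 of 2. Without B, the disagreement at 2 of 5 disappears and only 1 of 2 is left.

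Most of this stands, and it limits the practical harm. It does not make the printed condition correct or tell a reader which rule applied. The four rising doses suggest that the literal rule was not followed, but this is an inference, since neither document gives DLT counts or cohort sizes at the decisions. The protocol also still lists levels above 3×10^13 vg/kg and lets the DMC recommend more participants.

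**Conclusion.** The bullet is wrong as written. It permits no outcome at n = 2, 3 or 4, first permits 2 of 5, and never permits escalation from a cohort without DLTs. That much follows from the printed text alone. The intended rule cannot be recovered from the protocol and SAP. The three plausible readings agree on 0 of 2 and 2 of 2 and at n = 3 and 4; for n up to 5 they part only at 1 of 2 and 2 of 5, the latter only if B is entertained. The 9.5% to 42% range rests on assumed DLT probabilities of 5% to 30%; it measures how often the ambiguous outcome would arise, not how often a wrong decision would follow. No unsafe or non-compliant escalation is shown. The remaining consequence is for interpreting the dose path, because the adverse event outputs in SAP 6.1.1 and 6.6.1 include no DLT count by escalation decision.

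**What to change.** Replace the bullet with one computable condition. For example, under C: *The dose may be escalated only when 2 or more participants have been evaluated at the current level and the proportion with a DLT is 40% or lower.* Then 0 of 2 may escalate, 1 of 2 and 2 of 2 may not, and 2 of 5 may.

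If the paired threshold (A) was intended, say so: *The dose may not be escalated when the proportion with a DLT exceeds 40% and the number with a DLT is 2 or more.* Then 0 of 2, 1 of 2 and 2 of 5 are not barred, and 2 of 2 is.

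The sponsor must choose, and the wording should match the DMC charter. Because escalation appears complete, the CSR should state which rule was applied and give the DLT count and cohort size at each escalation decision.

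The cost is one reworded bullet, a check against the charter and one short CSR table.

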4.1.3. Early Termination

Participants who discontinue from the study prematurely or are withdrawn from the study will be asked to return to the study site for an Early Termination Visit (ETV). It is at the

discretion of the investigator to waive any procedures if they have been performed as part of standard of care within the standard interval of scheduled study visits per protocol. See the list of assessments to be performed at the ETV in the SoA ([Table 1](#)).

The investigator must make and document every attempt to ensure all participants are followed through the end of study (Month 60).

4.2. Scientific Rationale for Study Design

Hemophilia is an attractive target for gene therapy. This is due in part because minute-to-minute regulation of FVIII/Factor IX clotting protein (FIX) expression is not required (unlike proteins such as insulin). In addition, there is a wide therapeutic window for FVIII/FIX expression since therapeutic benefit can be achieved in severe hemophiliacs, who have FVIII/FIX activity <1%, with only modest improvements in factor expression. Any factor activity over 1% results in an improved phenotype (moderate hemophilia 1-5% or mild hemophilia 5-40%).

As the study was being planned, 1 adeno-associated virus (AAV)-mediated FVIII cDNA- and 5 AAV-mediated FIX cDNA-gene-transfer studies have been initiated and have reported at least some clinical study data. Details are provided in the Investigator's Brochure. Of the various AAV serotypes tested in the clinic, none have utilized the AAV6 serotype that will be tested in this clinical trial. Of the 4 studies where gene therapy was delivered intravenously, factor protein expression generally exhibited a dose response, though peak expression and durability of effect have been variable. Alanine aminotransferase (ALT) elevations due to AAV-associated transaminitis have been observed in at least 1 dose level in all studies reported to date using the IV route. AAV-associated transaminitis has been reported at vector doses ranging from 5×10^{11} vg/kg to 6×10^{13} vg/kg, with variable amount of losses in factor protein expression that may be associated with time to initiation of steroid therapy. Additional information on AAV-associated transaminitis is provided in Section [10.7](#).

4.2.1. Rationale for Use of rAAV2/6 Serotype Based on Preclinical Studies

The rAAV2/6 serotype was selected for use in Sangamo gene therapy platforms based on previous NHP data showing that AAV2/6 was primarily hepatotropic, with similar biodistribution to AAV2/8 and that AAV2/6 and AAV2/8 vectors yielded similar levels of circulating FIX transgene expression (see the Investigator's Brochure).

4.3. Justification for Dose

The rationale for SB-525 (PF-07055480) dose selection was based on (i) the dose-response relationship of circulating levels of human FVIII generated in NHP following a single IV dose administration of SB-525 (PF-07055480), (Sangamo Study Number TX16-HMA-008); (ii) preclinical dose ranging safety studies (2×10^{11} to 2×10^{13} vg/kg) in mice and NHP resulting in no adverse events (AEs), histological changes or tumorigenicity; and (iii) recently published clinical trials involving similar cDNA-based strategies (see the Investigator's Brochure). The proposed clinical dose range is 6×10^{11} to 6×10^{13} vg/kg, with a starting dose of 9×10^{11} vg/kg, which was associated with FVIII activity of 12% of normal

in an NHP study. The 6×10^{11} dose is an optional de-escalation dose level if FVIII activity in humans is much higher than observed in NHPs.

Although the translation of SB-525 (PF-07055480) pharmacodynamics (PD); delivery to liver, transduction, and FVIII expression) from NHP to humans is unknown, the dose escalation assumes a direct translation between species with starting low dose levels expected to result in therapeutic FVIII levels. Subsequent doses will follow an adaptive dose escalation or de-escalation plan to mitigate the possibility that the human efficacious dose is higher than observed in NHP.

A population kinetic-PD model incorporated the monkey plasma human FVIII data with the assumption that the NHP response models human response in terms of plasma FVIII levels. With this model, a clinical starting dose of 9×10^{11} vg/kg is expected to yield >5% normal FVIII levels in 57% of treated participants. This is a reasonable target for the starting dose. Further information of the dose escalation plan is found in Section 4.1.2.

4.4. End of Study Definition

A participant is considered to have completed the study if he has completed all phases of the study including the End-of-Study (EOS) visit (Month 60).

The end of the study is defined as the date of the EOS Visit of the last participant in the study.

5. STUDY POPULATION

This study can fulfill its objectives only if appropriate participants are enrolled. The following eligibility criteria are designed to select participants for whom participation in the study is considered appropriate. All relevant medical and nonmedical conditions should be taken into consideration when deciding whether a particular participant is suitable for this protocol.

Prospective approval of protocol deviations to recruitment and enrollment criteria, also known as protocol waivers or exemptions, is not permitted.

5.1. Inclusion Criteria

Participants are eligible to be included in the study only if all of the following criteria apply:

1. Signed informed consent.
2. Male ≥ 18 years of age able to understand the informed consent.
3. Severe hemophilia A (with past evidence of circulating FVIII activity of <1% normal).
4. Treated or exposed to FVIII concentrates or cryoprecipitate for at least 150 exposure days.
5. ≥ 12 bleeding episodes if receiving on-demand therapy over the preceding 12 months.

6. Sexually active participants must agree to use double barrier contraceptive (one of them being a condom) or abstinence, and all participants must refrain from donating their sperm until at least 3 consecutive semen samples after SB-525 (PF-07055480) treatment are negative for AAV2/6 and for a minimum of 90 days after SB-525 (PF-07055480) administration.

5.2. Exclusion Criteria

Participants are excluded from the study if any of the following criteria apply:

1. Neutralizing activity to AAV6 capsid.
2. Current inhibitor, or history of FVIII inhibitor (except for transient low titer inhibitor detected in childhood).
3. History of hypersensitivity response to FVIII.
4. History of hepatitis B or HIV-1/2 infection.
5. History of hepatitis C, unless viral assays in 2 samples, collected at least 6 months apart, are negative.
6. Two (2) or more occurrences of any of the following: hemoglobin <10g/dL, platelets <100,000/ μ L, or white blood cells less than 4,000 cells/ μ L.
7. Evidence of any bleeding disorder in addition to hemophilia A.
8. History of tuberculosis or systemic fungal disease.
9. Symptomatic cardiovascular disease as a co-morbid condition.
10. Markers of hepatic inflammation or overt or occult cirrhosis as evidenced by 1 or more of the following:
 - Albumin \leq 3.5 g/dL;
 - Total bilirubin $>$ 1.5 x ULN and direct bilirubin \geq 0.5 mg/dL;
 - Alkaline phosphatase $>$ 2.0 \times ULN;
 - ALT or aspartate aminotransferase (AST) $>$ 1.3 \times ULN;
 - International Normalized Ratio (INR) $>$ 1.5.
11. History of chronic renal disease or creatinine \geq 1.5 mg/dL.
12. Use of systemic (IV or oral) immunomodulatory agent or steroid use within 3 months prior to screening (inhaled or topical treatment is allowed, eg, for asthma or eczema).

13. History of chronic infection or other chronic disorder considered an unacceptable risk.
14. Presence of liver mass on magnetic resonance imaging (MRI) or any equivalent imaging technology, or, positive alpha fetoprotein.
15. Presence of >Grade 2 liver fibrosis on elastography (or any equivalent imaging technology) for participants with history of treated Hepatitis C or suspicion of chronic liver disease.
16. History of malignancy except for successfully treated basal cell carcinoma.
17. History of alcohol or substance abuse.
18. Any contraindication to the use of corticosteroids.
19. Previously received gene therapy product.
20. Participation in prior investigational drug or medical device study within 3 months prior to screening.
21. History of therapeutic non-adherence.
22. Any other reason that, in the opinion of the investigator or medical monitor, would render the participant unsuitable for participation in the study.

5.3. Lifestyle Considerations

Sexually active patients should use 1 of the acceptable forms of contraceptives described in [Appendix 4](#) (Section 10.4).

5.4. Screen Failures

Screen failures are defined as participants who consent to participate in the clinical study but are not subsequently entered in the study. A minimal set of screen failure information is required to ensure transparent reporting of screen failure participants to meet the Consolidated Standards of Reporting Trials (CONSORT) publishing requirements and to respond to queries from regulatory authorities. Minimal information includes demography, screen failure details, eligibility criteria, and any SAE.

Individuals who do not meet the criteria for participation in this study (screen failure) may be rescreened. Rescreened participants are required to sign a new ICF and will be assigned a different participant number.

6. STUDY INTERVENTION

Study intervention is defined as any investigational intervention(s), marketed product(s), placebo, or medical device(s) intended to be administered to a study participant according to the study protocol.

For the purposes of this protocol, study intervention refers to SB-525 (PF-07055480).

6.1. Study Intervention(s) Administered

ARM Name	Single arm study
Intervention Name	PF-07055480
Type	Gene therapy
Dosage Form	Injectable
Dose Strength	6×10^{11} , 9×10^{11} , 1.2×10^{12} , 2×10^{12} , 4×10^{12} , 6×10^{12} , 1×10^{13} , 2×10^{13} , 3×10^{13} , 4×10^{13} , 5×10^{13} , 6×10^{13} vg/kg
Dosage	Single infusion Several dose levels may need to be studied to identify a safe and tolerable therapeutic range. For a participant with BMI >30 kg/m ² , dose will be calculated based on an adjusted body weight determination that assumes a maximum permissible BMI of 30 kg/ m ² , eg, for 187.96 cm (6'2") height and 167.8 kg weight (BMI 47.5 kg/m ²) dose will be based on 106.1 kg, which is the weight associated with a BMI of 30 kg/m ² for a 187.96 cm (6'2") tall individual
Route of Administration	Intravenous infusion/injection
IMP and NIMP	IMP (investigational medicinal product)
Sourcing	Provided centrally by the sponsor.
Packaging and Labeling	Study Intervention will be provided in a 4.7 mL/vial. Each vial will be labeled as required per country requirement.
Current/Former Name(s) or Alias(es)	PF-07055480 SB-525 Adeno-associated viral vector with human factor VIII gene

